8.1.1 Study Design

Single arm un-blinded non-randomized Phase II study.

8.1.2 Randomization

No randomization is planned.

8.1.3 Un-blinding Subjects

No blinding is planned.

8.1.4 Stratification Factors

No stratification is required; all patients will receive the same treatment and follow the same assessment procedures.

8.2 Determination of Sample Size and Accrual Rate

Based on historical controls, we estimate accrual of 12 patients per year, with a goal of 24 patients by 2 years.

8.2.1 Sample Size and Power Estimate

Assuming an historical rate of severe TMA of 28%, alpha=5%, and N=24, power to detect a statistically significant value of 4% in this cohort is 92%. The minimum number of patients to enroll to achieve 80% power to detect a difference, assuming a 4% incidence in this cohort, is N=19. Assuming a sample size of N=24, the study has 80% power to detect a statistically significant difference if the incidence of severe TMA in this treated cohort is <5%. Given the small sample size, adjustments for multiple comparisons will not be made.

8.2.2 Replacement Policy

Patients that discontinue participation for reasons other than direct defibrotide toxicity or failure of feasibility will be replaced with additional patients. This included patients who are no longer evaluable for TMA due to mortality prior to week 24.

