1.1 Background on Indication

Hematopoietic stem cell transplant (HSCT) is associated with an appreciable degree of transplant-related (i.e. toxic) mortality (TRM). The incidence of TRM at 1-year post-HSCT ranges from 5-15% depending upon the stem cell source utilized (Wingard, J Clin Oncol 2011). The UCSF BCH-SF BMT program has reviewed all cases of non-relapse related death from 2012-2015 and identified a complication of endothelial injury known as transplant associated thrombotic microangiopathy (TMA) as the most common cause of TRM in our patient population.

TMA is a multi-system disease in which widespread endothelial injury leads to microangiopathic hemolytic anemia, intravascular platelet activation and formation of thrombi within the microcirculation. The endothelial injury then promotes the complement cascade leading to additional injury to the endothelium further propagating the disorder.

TMA predominantly occurs in the kidneys but can affect the liver, lungs, intestines and brain. The risk factors for the development of TMA include myeloablative and reduced intensity conditioning regimens, calcineurin inhibitors (tacrolimus, cyclosporine), mTOR inhibitors (sirolimus), and infections. Additional risk factors include mismatched donors, ABO mismatch, and non-Caucasian patients. When genetic testing was performed looking at seventeen genes involved in the pathogenesis of other thrombotic microangiopathies, non-Caucasian patients with TMA were found to have more genetic variations when compared Caucasian patients (Jodele, Blood 2016).

Diagnosis of TMA can be difficult as systemic signs and symptoms of TMA are often similar to other common transplant complications, such as medication induced hypertension and cytopenias. Unlike in thrombocytopenic purpura, patients with TMA have normal ADAMTS13 activity. A renal biopsy would be useful in diagnosis however is often not possible given the risk factors of the procedure in a transplant patient.

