1.3 Rationale for the Proposed Study

Upon retrospective review of our cases of TMA and the medical literature, we are now classifying patients as either standard-risk for the development of TMA, or high-risk, based on the following clinical criteria:

1. Patients undergoing tandem autologous transplant with thiotepa in one or more of the conditioning regimens.

OR:

2. Patients with at least 3 of the following characteristics:
 - a) >10 years of age
 - b) Non-Caucasian race/ Hispanic ethnicity
 - c) Undergoing haploidentical transplant
 - d) Minor ABO Mismatch

Using these criteria, we retrospectively reviewed 160 transplants performed from 1/1/13 to 9/30/16. There were 13 cases of TMA total (8.1%), with 7 cases (4.4%) deemed severe by the onset of renal failure, development of pericardial effusion, and/or death. In the 138 standard-risk patients, there were 6 total cases of TMA, but only 1 was severe (0.7%). Conversely, in the 22 high-risk patients there were 7 total TMA cases, 6 of which were severe (27.3%). Most cases showed evidence of evolving TMA before Day +100 post-HCT, and some cases of TMA were evident within a week following HCT.

Several groups have demonstrated that the onset of endothelial injury and clinical TMA typically begins within 4-6 weeks following HCT (Jodele Blood Rev 2015, Obut BMT 2016). Therefore, the hypothesis is that in high-risk patients the administration of certain combinations of high-dose conditioning agents (radiation and/or chemotherapy) and/or post-HSCT inflammatory events initiate the complement pathway to aberrantly attack the endothelium. Although the current standard treatment for post-transplant microangiopathic processes involves targeting inflammatory mediators with complement blockade and plasmapheresis, these therapies do not address the prevention or treatment of the initial pathologic trigger, namely, endothelial damage.

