2.2 Secondary

- To determine if administration of prophylactic Defibrotide will prevent the development of TMA in clinically high-risk patients compared to historic controls.
 - Incidence of TMA in the first 6 months post-HSCT will be compared to incidence in a similar cohort of historical controls.
 - Incidence of severe TMA as defined by any TMA with the following complications:
 - Renal dysfunction requiring dialysis
 - Pleural or pericardial effusion requiring any medical or surgical intervention
 - CNS dysfunction including seizure, PRES
 - Death

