3.5 Duration of Follow Up

Patients will be followed for 6 months post-HSCT, or until death, whichever occurs first. Patients removed from study for unacceptable treatment related adverse event(s) will be followed until resolution or stabilization of all treatment-related adverse events to Grade 2 or lower.

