8.4 Analyses Plans

8.4.1 Analysis Population

The analysis population will include all the patients who enroll that receive defibrotide.

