8.4.3 Secondary Analysis (or Analysis of Secondary Endpoints)

This will include the incidence of TMA in the patients enrolled on study compared to historical controls, including their demographics, underlying diagnosis, conditioning regimens and other transplant complications. Also will compare incidence of severe TMA compared to historical controls and the complications.

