8.4.4 Other analyses/Assessments

Other analysis include incidence of TMA by Day +30 post-HSCT, non-relapse mortality by Day +100 and by Day +180 post-HSCT. Summaries for biomarkers will be provided. Additional exploratory analyses may be performed based on incidence of elevation of single or combination of biomarkers predictive of development of TMA.

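### Severe TMA is defined differently on study (7.2.2) and in the historical 6/22 it is compared with (1.3), and 2.2 and 7.2.2 disagree on death

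*Combined protocol and SAP*

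**What the plan says.** **Severe TMA.** Section 1.3 reports 7 TMA cases in 22 high-risk patients, 6 of them severe (27.3%). It describes the historical severe cases as "deemed severe by the onset of renal failure, development of pericardial effusion, and/or death". Objective 2.2 sets out the "Incidence of severe TMA as defined by any TMA with the following complications", and its list includes death. Section 2.4.2 sends the reader to 7.2.2 for the endpoint, and the list in 7.2.2 does not include death. Sections 8.1 and 8.4.3 compare the on-study rate with historical controls. Section 8.1 uses 6/22, and 8.2.1 bases its power on 28%.

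**Early deaths.** Section 8.2.2 replaces patients who stop for reasons other than defibrotide toxicity or failure of feasibility, and adds: "This included patients who are no longer evaluable for TMA due to mortality prior to week 24". Section 8.4.1 states: "The analysis population will include all the patients who enroll that receive defibrotide". Section 8.4.2 names an ITT population for efficacy, and 8.4.3 compares the "incidence of TMA in the patients enrolled on study compared to historical controls". Section 3.5 treats death as a planned end of observation: "Patients will be followed for 6 months post-HSCT, or until death, whichever occurs first".

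**The concern.** A comparison with historical controls needs the event counted in the same way on both sides. Here a patient with TMA who dies with no other listed feature is severe under 1.3 and 2.2 but not under 7.2.2. That is not a remote case: 1.1 identifies TMA "as the most common cause of TRM in our patient population", and the background cites mortality of 30-50% in TMA and up to 80% in severe disease. Death is also not the only difference, so the treated rate and the 27.3% benchmark do not measure the same thing. The two TMA rates are the only comparisons with a power statement, and with 24 patients significance turns on one or two events.

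The wording of 8.2.2 raises a smaller question. It calls patients who die before week 24 not evaluable for TMA, makes no exception for those who died with TMA, and does not say how they enter the TMA rates.

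**Working it through.** **Inputs.** From 1.3: 22 high-risk patients, 7 with TMA, 6 severe; 13 TMA cases in all 160 transplants. From 8.2.1: N=24, historical rate 28%, alpha 5%, target 4%, power 92%. The plan names no test and no sidedness. I use the exact one-sample binomial test (two-sided p is the sum of the probabilities of all outcomes no more likely than the one observed), with Fisher's exact test against the 22 controls as a cross-check.

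**Step 1: the plan's own figure.** P(X≤2 | 24, 0.28) = 0.020 and P(X≤3 | 24, 0.28) = 0.064, so the cut-off is 2 events. Power at 4% is P(X≤2 | 24, 0.04) = 93.1%. The two-sided normal approximation gives 93.4%, with 80.2% at N=19 and 76.0% at N=18. The stated 92% and minimum of 19 reproduce closely. The problem is not a power error in 8.2.1.

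**Step 2: the three definitions side by side.**

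| Feature | 1.3 (historical) | 2.2 (objective) | 7.2.2 (endpoint) | 7.2.2 against 1.3 |
|---|---|---|---|---|
| Kidney | renal failure | dialysis needed | dialysis needed | narrower |
| Pericardial effusion | any | needing intervention | needing intervention | narrower |
| Pleural effusion | not listed | needing intervention | needing intervention | wider |
| CNS | not listed | yes; seizure and PRES named | yes; seizure named, PRES not | wider |
| Death | yes | yes | not listed | narrower |
| TMA-related admission > 90 days | not listed | not listed | yes | wider |

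Three rows make an event less likely to count on study and three make it more likely. The documents do not give the net effect.

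**Step 3: one treated case graded differently**, against 6/22.

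| Severe cases / 24 | Exact two-sided p | Fisher two-sided p |
|---|---|---|
| 0 | 0.0008 | 0.008 |
| 1 | 0.010 | 0.043 |
| 2 | 0.038 | 0.128 |
| 3 | 0.114 | 0.276 |

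One fatal TMA case not graded severe turns 3/24 into 2/24 and p=0.114 into p=0.038. Under Fisher the same happens between 2/24 and 1/24. With no case counted, adding one leaves both tests significant.

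**Step 4: historical cases graded differently.** Section 1.3 does not split the six cases by criterion, so the shifts are assumed. The ceiling is 7/22, because only 7 high-risk patients had TMA.

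| Benchmark under 7.2.2 | Exact p for 2/24 | Largest significant count (two-sided) | Power at 4% |
|---|---|---|---|
| 7/22 = 31.8% | 0.014 | 3 (p=0.048) | 98.6% |
| 6/22 = 27.3% | 0.038 | 2 | 93.1% |
| 5/22 = 22.7% | 0.140 | 1 (p=0.027) | 75.1% |
| 4/22 = 18.2% | 0.293 | 0 (1/24 gives p=0.107) | 37.5% |

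Power is P(X≤c | 24, 0.04), with c the count in the third column. For c=1 it is 0.96^24 + 24 × 0.04 × 0.96^23 = 0.375 + 0.375 = 0.751. For c=0 it is 0.96^24 = 0.375.

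**Step 5: early deaths.** Section 8.2.2 sits under sample size and accrual and speaks of additional patients. The rules for who is analysed are in 8.4.1 to 8.4.3, and none removes a dosed patient who dies. On the control side, 138 + 22 = 160, so every reviewed transplant is in a denominator. Read this way, the two denominators agree and replacement only raises N above 24.

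**The case against.** **This is secondary, and 8.1 already covers it.** The primary endpoints are feasibility and safety. Section 8.1 says that a single severe case makes the severe-TMA endpoint futile, and every change of conclusion in step 3 starts from at least one counted case. Both points stand and limit the weight of this one. They do not remove it: 8.1 lets enrolment continue or the cohort expand, 8.4.3 plans the comparison without any condition, and the benchmark enters the power statements whatever count is observed.

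**Section 1.3 may only summarise how the cases presented.** That is possible. But nothing in the documents shows that the historical cases were graded by 7.2.2, and the conflict between 2.2 and 7.2.2 remains on either reading.

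**Two stronger readings are tempting.** A reader might infer that 8.2.2 drops early deaths from the analysis, so that the treated rate is conditional on survival. The documents do not support this: 8.4.1 keeps all dosed patients, 8.4.2 cites ITT and 8.4.3 uses enrolled patients. A patient diagnosed with TMA before death has also been evaluated. A reader might also infer that the definition mismatch favours defibrotide. The missing death criterion does, taken alone, but the features added in 7.2.2 work the other way, and no historical case is documented as severe by death alone.

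**Conclusion.** The definition mismatch holds and is wrong as written: following 2.4.2 and 7.2.2 compares the treated cohort with a rate obtained under different criteria, and the protocol gives two answers on whether death makes TMA severe. The direction is unknown. As to size, one patient graded differently on either side can move 2/24 across the 5% line, and one historical case fewer would lower the exact power at 4% from 93.1% to 75.1%. These figures rest on a test that the plan does not name and on assumed shifts of one or two historical cases; no shift at all is equally consistent with the text. The primary safety and feasibility endpoints are not affected.

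On 8.2.2, no exclusion bias is shown. The not-evaluable label only needs a clarifying sentence or two.

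**What to change.** 1. Reconcile 2.2 and 7.2.2 into one definition of severe TMA that says explicitly whether death with TMA counts and whether PRES is included. Settling death alone is not enough, because the renal, effusion, CNS and admission criteria also differ from 1.3.
2. Re-grade the 13 historical TMA cases (7 of them high-risk) by that definition, and report the count meeting each criterion.
3. If the rate changes from 6/22, restate the benchmark in 1.3 and the power in 8.1 and 8.2.1.
4. Minor: say in 8.2.2 that replacement patients are added, not substituted; that every dosed patient stays in the 8.4.1 population; that TMA present before or at death is an event; and that TMA-free deaths before week 24 stay in the denominator, as in the historical 22, with their number reported. Section 8.4.4 already plans "non-relapse mortality by Day +100 and by Day +180 post-HSCT".

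The cost is a few sentences and a short review of existing records. The drawbacks are that the benchmark may become less favourable to the comparison, that N may exceed 24, and that patients who die early contribute less than 6 months of observation.

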8.2.3 Accrual estimates

Based on historical rates we estimate accrual of 12 patients per year.

8.3 Interim Analyses and Stopping Rules

Stopping rules as described in section 8.1.

8.4 Analyses Plans

8.4.1 Analysis Population

The analysis population will include all the patients who enroll that receive defibrotide.

8.4.2 Primary Analysis (or Analysis of Primary Endpoints)

The primary efficacy analysis will be performed using the ITT population. The primary endpoint will assess the safety and feasibility of defibrotide. It will compare how many patients received the drug versus how many were intended to receive it. It will look into how many patients stopped the drug early and reasons for this.

8.4.3 Secondary Analysis (or Analysis of Secondary Endpoints)

This will include the incidence of TMA in the patients enrolled on study compared to historical controls, including their demographics, underlying diagnosis, conditioning regimens and other transplant complications. Also will compare incidence of severe TMA compared to historical controls and the complications.

8.4.4 Other analyses/Assessments

Other analysis include incidence of TMA by Day +30 post-HSCT, non-relapse mortality by Day +100 and by Day +180 post-HSCT. Summaries for biomarkers will be provided. Additional exploratory analyses may be performed based on incidence of elevation of single or combination of biomarkers predictive of development of TMA.

8.5 Evaluation of Safety

Analyses will be performed for all patients having received at least one dose of study drug. The study will use the NCI CTCAE v4.03.

8.6 Study Results

Study results will be made available on ClinicalTrials.gov and will be published once the study has completed enrollment and all patients have completed the required follow-up period.

9 Study Management

9.1 Pre-study Documentation

This study will be conducted in accordance with the ethical principles that have their origin in the Declaration of Helsinki as stated in 21 CFR §312.120(c)(4); consistent with GCP and all applicable regulatory requirements.

Before initiating this trial, the Investigator will have written and dated approval from the Institutional Review Board for the protocol, written informed consent form, subject recruitment materials, and any other written information to be provided to subjects before any protocol related procedures are performed on any subjects.

The clinical investigation will not begin until either FDA has determined that the study under the Investigational Drug Application (IND) is allowed to proceed or the Investigator has received a letter from FDA stating that the study is exempt from IND requirements.

The Investigator must comply with the applicable regulations in Title 21 of the Code of Federal Regulations (21 CFR §50, §54, and §312), GCP/ICH guidelines, and all applicable regulatory requirements. The IRB must comply with the regulations in 21 CFR §56 and applicable regulatory requirements.

9.2 Institutional Review Board Approval

The protocol, the proposed informed consent form, and all forms of participant information related to the study (e.g. advertisements used to recruit participants) will be reviewed and approved by the UCSF CHR (UCSF Institutional Review Board). The initial protocol and all protocol amendments must be approved by the IRB prior to implementation.

9.3 Informed Consent

All participants must be provided a consent form describing the study with sufficient information for each participant to make an informed decision regarding their participation. Participants must sign the CHR-approved informed consent form prior to participation in any study specific procedure. The participant must receive a copy of the signed and dated consent document. The original signed copy of the consent document must be retained in the medical record or research file.

9.4 Changes in the Protocol

Once the protocol has been approved by the UCSF CHR, any changes to the protocol must be documented in the form of an amendment. The amendment must be signed by the Investigator and approved by the CHR prior to implementation.

If it becomes necessary to alter the protocol to eliminate an immediate hazard to patients, an amendment may be implemented prior to CHR approval. In this circumstance, however, the Investigator must then notify the CHR in writing within five (5) working days after implementation. The Study Chair and the UCSF study team will be responsible for updating any participating sites.

9.5 Handling and Documentation of Clinical Supplies

The UCSF Principal Investigator and each participating site will maintain complete records showing the receipt, dispensation, return, or other disposition of all investigational drugs. The date, quantity and batch or code number of the drug, and the identification of patients to whom study drug has been dispensed by patient number and initials will be included. The sponsor-investigator will maintain written records of any disposition of the study drug.

The Principal Investigator shall not make the investigational drug available to any individuals other than to qualified study patients. Furthermore, the Principal Investigator will not allow the investigational drug to be used in any manner other than that specified in this protocol.

9.6 Case Report Forms (CRFs)

The Principal Investigator and/or his/her designee, will prepare and maintain adequate and accurate participant case histories with observations and data pertinent to the study. Study specific Case Report Forms (CRFs) will document safety and treatment outcomes for safety monitoring and data analysis. All study data will be entered into the study database via standardized CRFs in accordance with the CTMS study calendar, using single data entry with a secure access account. The Clinical Research Coordinator (CRC) will complete the CRFs as soon as possible upon completion of the study visit; the Investigator will review and approve the completed CRFs.

The information collected on CRFs shall be identical to that appearing in original source documents. Source documents will be found in the patient's medical records maintained by UCSF personnel. All source documentation should be kept in separate research folders for each patient.

In accordance with federal regulations, the Investigator is responsible for the accuracy and authenticity of all clinical and laboratory data entered onto CRFs. The PI will approve all completed CRFs to attest that the information contained on the CRFs is true and accurate.

All source documentation and CTMS data will be available for review/monitoring by regulatory agencies.

The Principal Investigator will be responsible for ensuring the accurate capture of study data. At study completion, when the CRFs have been declared to be complete and accurate, the database will be locked. Any changes to the data entered into the CRFs after that time can only be made by joint written agreement among the Study Chair, the Trial Statistician, and the Protocol Project Manager.

9.7 Oversight and Monitoring Plan

The CHR will audit study-related activities to ensure that the study is conducted in accordance with the protocol, local standard operating procedures, FDA regulations, and Good Clinical Practice (GCP). Coordinating Center Documentation of Distribution

It is the responsibility of the Study Chair to maintain adequate files documenting the distribution of study documents as well as their receipt (when possible). Correspondence file: should contain copies (paper or electronic) of all protocol versions, cover letters, amendment outlines (summary of changes), etc., along with distribution documentation and (when available) documentation of receipt.

Correspondence log: should be a brief list of all documents distributed including the date sent, recipient(s), and (if available) a tracking number and date received.

At a minimum, the Study Chair must keep documentation of when and to whom the protocol, its updates and safety information are distributed.

